3.4.1.2.2. Systemic Events

The presence of systemic events (fatigue, headache, vomiting, diarrhea, muscle pain, and joint pain) will be recorded in the e-diary daily for 7 days (Day 1 through Day 7, where Day 1 is the day of vaccination) after vaccination, using the grading scale in Table 7 below.

If a systemic event persists beyond the end of the e-diary period, the subject’s parent(s)/legal guardian(s)/caregiver(s) will be requested to report that information and/or any new AEs that develop to the investigator. The investigator will enter this additional information in the CRF.

Table 7. Grading Scale for Systemic Events

| | Mild Grade 1 | Moderate Grade 2 | Severe Grade 3 |
|-------------------------------------|----------------------------------|---------------------------------|------------------------------------|
| Fatigue (= tiredness in diaries) | Does not interfere with activity | Some interference with activity | Prevents daily routine activity |
| Headache | Does not interfere with activity | Some interference with activity | Prevents daily routine activity |
| Vomiting | 1 to 2 times in 24 hours | More than 2 times in 24 hours | Requires intravenous hydration |
| Diarrhea | 2 to 3 loose stools in 24 hours | 4 to 5 loose stools in 24 hours | 6 or more loose stools in 24 hours |
| Muscle pain | Does not interfere with activity | Some interference with activity | Prevents daily routine activity |
| Joint pain | Does not interfere with activity | Some interference with activity | Prevents daily routine activity |

For fatigue (synonymous with tiredness in the e-diaries), headache, muscle pain, and joint pain on each day, an indicator variable will be created for them for each day separately, using the following algorithm:

- = ●, if fatigue, headache, muscle pain, or joint pain is missing
- = 0 (none), if no fatigue, headache, muscle pain, or joint pain
- = 1 (mild), if does not interfere with activity
- = 2 (moderate), if some interference with activity
- = 3 (severe), if prevents daily routine activity

For vomiting on each day, an indicator variable will be created for each day using the following algorithm:

- = ●, if vomiting is missing
- = 0 (none), if no vomiting
- = 1 (mild), if 1 to 2 times in 24 hours
- = 2 (moderate), if more than 2 times in 24 hours
- = 3 (severe), if requires intravenous hydration

For diarrhea on each day, an indicator variable will be created for each day using the following algorithm:

- = ●, if diarrhea is missing
- = 0 (none), if no diarrhea
- = 1 (mild), if 2 to 3 loose stools in 24 hours
- = 2 (moderate), if 4 to 5 loose stools in 24 hours
- = 3 (severe), if 6 or more loose stools in 24 hours

For the systemic events, 3 more derivations are required: whether or not a specific reaction occurs on any day, whether or not the subject experiences any other systemic event on a given day, and whether or not the subject experiences any other systemic events on any day. Similar algorithms described in [Section 3.4.1.1](#) will be used.

3.5. Study Conduct

3.5.1. E-Diary Completion

An e-diary will be considered transmitted if any data for the local reactions or the systemic events are present on any day. If all data are missing for all items on the e-diary for all 7 days following vaccination, then the e-diary will be considered not transmitted.

For transmitted e-diaries, the following variables will be defined: “Day 1,” “Day 2,” “Day 3,” “Day 4,” “Day 5,” “Day 6,” “Day 7,” and “Day 1 – Day 7.”

An e-diary will be considered completed if all expected data for all 7 days are available (ie, not missing) and data are valid. Otherwise, the e-diary will be considered incomplete.

For any given day, an e-diary will be considered complete if all expected data are available.

For completed e-diaries, the following variables will be defined: “Day 1,” “Day 2,” “Day 3,” “Day 4,” “Day 5,” “Day 6,” “Day 7,” and “Day 1 – Day 7.”

For e-diaries that are incomplete, an indicator variable for the percentage of days without data will be derived as follows:

- = 1, if data have been transmitted, and are complete for 7 days (100%)
- = 2, if data have been transmitted, and are complete for 6 days ($\geq 75\%$ to $< 100\%$)
- = 3, if data have been transmitted, and are complete for 4 or 5 days ($\geq 50\%$ to $< 75\%$)
- = 4, if data have been transmitted, and are complete for 2 or 3 days ($\geq 25\%$ to $< 50\%$)
- = 5, if data have been transmitted, and are complete for 0 or 1 day ($< 25\%$)

3.5.2. Demographic, Medical History, and Baseline Characteristics Variables

The demographic variables are age at first vaccination visit (in years) at Visit 1, sex, race, and ethnicity. Age will be calculated as $(\text{first vaccination date} - \text{date of birth} + 1)/365.25$ and rounded to 1 decimal place. Medical history will be categorized according to the Medical Dictionary for Regulatory Activities (MedDRA).

Clinically significant findings for physical examination will be recorded as yes or no in the CRF.

3.5.3. Nonstudy Vaccinations

Nonstudy vaccines will be categorized according to the World Health Organization (WHO) Drug Dictionary (WHODD).

3.5.3.1. Concomitant Vaccines and Medication(s)

3.5.3.1.1. Prohibited During the Study

The following are prohibited during the study:

- Vaccination with any licensed or investigational pneumococcal vaccine other than that specified by the protocol.
- Receipt of any other investigational product.

3.5.3.1.2. Permitted During the Study

The following are permitted during the study:

- Any other vaccine may be given according to local practice. If any vaccine other than 13vPnC is administered during the study, the name and date of administration will be documented in the CRF.
- Any medication, except those listed in Section 3.5.3.1.1, is permitted but will not be documented in the CRF.

4. ANALYSIS SETS

Data for all subjects will be assessed to determine if subjects meet the criteria for inclusion in each analysis population prior to unblinding and releasing the database and classifications will be documented per standard operating procedures.

4.1. Full Analysis Set

The full analysis set (FAS) is all subjects who have been enrolled in the study, regardless of whether or not investigational product was received.

4.2. Safety Analysis Set

The safety population will include all subjects who receive 1 dose of an investigational product.

4.3. Other Analysis Sets

Not applicable.

5. GENERAL METHODOLOGY AND CONVENTIONS

5.1. Hypotheses and Decision Rules

No formal statistical hypothesis test will be performed as this is a descriptive study and no formal hypotheses were predetermined. There are also no formal statistical decision rules for this study and a descriptive estimation approach will be used to assess all study objectives regarding safety in the study.

Point estimates and nominal 95% confidence intervals (CIs) will be provided for all safety endpoints at each planned analysis.

No formal multiplicity adjustments will be applied due to multiple endpoints or multiple looks of the same endpoint.

5.2. General Methods

Unless otherwise explicitly stated, descriptive statistics for continuous variables are n, mean, median, standard deviation, minimum, and maximum. Descriptive statistics for categorical variables are the percentage (%) and the numerator (n) and the denominator (N) used in the percentage calculation.

5.2.1. Analyses for Binary Data

The exact CIs (Clopper-Pearson) for the various proportions of individual groups will be computed using the F distribution. If r is the number of responses and n is the number of subjects, then it follows that $p=r/n$ is the estimate of the proportion of responses. An exact 95% CI can be computed by solving the following 2 equations. For the lower limit P_L ,

$$P_L = \frac{rF_L}{(rF_L + (n - r + 1))}$$

and for the upper limit P_U ,

$$P_U = \frac{(r + 1)F_U}{(n - r) + (r + 1)F_U}$$

where F_L is the quantile from the F distribution for $\alpha=0.025$, with numerator degrees of freedom equal to $2r$ and denominator degrees of freedom equal to $2(n-r+1)$. F_U is the quantile from the F distribution for $\alpha=0.975$, with numerator degrees of freedom equal to $2(r+1)$ and denominator degrees of freedom equal to $2(n-r)$. When r equals 0, F_L should be set equal to 1.0 so P_L equals 0. When r equals n, F_U should be set equal to 1.0 so P_U equals 1.0.

The CI using the F distribution is described in [Collett \(1991\)](#) and implemented in SAS PROC FREQ.

5.3. Methods to Manage Missing Data

5.3.1. Safety Data

Handling of missing information related to safety data, such as missing or partially missing date, will be in accordance with Pfizer reporting standards.

For derived variables in reactogenicity data, if any day of the 7-day e-diary is available, the “Day 1 – Day 7” data will be considered as nonmissing for analyses after vaccination. The proportion of subjects with missing reactogenicity data will also be summarized. The denominator will be the number of subjects who receive the scheduled vaccination.

6. ANALYSES AND SUMMARIES

6.1. Primary Endpoint(s)

6.1.1. Safety Endpoints

6.1.1.1. Primary Analysis

Endpoints: Safety endpoints in [Section 3.1](#)

- Analysis time points:

Endpoints for local reactions and systemic events: 7 days after each vaccination

Endpoints for AEs and SAEs: from the signing of the informed consent document (ICD) to 1 month after vaccination

- Analysis population: Safety population
- Analysis methodology: Descriptive; also see [Section 5.2.1](#)
- Supporting objective: Primary objective

Reporting results:

The number, proportion, and corresponding 95% CI will be presented.

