2. STUDY OBJECTIVES AND ENDPOINTS

Primary Objective(s):	Primary Endpoint(s):
To describe the safety profile of 13vPnC in pediatric subjects 6 to 17 years of age.	
Local reactions within 7 days after vaccination.Systemic events within 7 days after vaccination.AEs within 1 month after vaccination.

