6. STUDY PROCEDURES

The schedule of procedures for individual study participation is summarized in the Schedule of Activities. In order that the study visits are scheduled within the correct time frames, the day of vaccination should be considered Day 1.

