6.1. Visit 1 - Vaccination (Day 1)

- Obtain written informed consent and, if applicable, assent (age dependent on local requirement) before performing any study-specific procedures.
- Assign a subject identification number.
- Obtain and record the subject demography (including date of birth, sex, race, and ethnicity).
- Obtain and record any nonstudy vaccinations received from 28 days prior to vaccination.
- Obtain and record the medical history, including the presence of chronic conditions and/or medical history of significance.
- Perform physical examination evaluating any clinically significant abnormalities, including worsening of medical history conditions, within the following body systems: general appearance; skin; head, eyes, ears, nose, and throat; heart; lungs; abdomen; musculoskeletal; extremities; neurological; and lymph nodes.
- Collect and record any AEs and serious adverse events (SAEs) that occurred since the signing of the ICD.
- Perform a urine pregnancy test on female subjects of childbearing potential.
- Confirm use of appropriate contraceptives (if appropriate).
- On the day of vaccination, prior to vaccination, measure and record the subject's temperature using the preferred local method.
- Ensure that all of the inclusion criteria, none of the exclusion criteria, and none of the temporary delay criteria are met.
- Administer a single 0.5-mL injection of 13vPnC into the left thigh or the left deltoid muscle as appropriate for the subject.
- Observe the subject for at least 20 minutes after 13vPnC administration for any acute reactions. Record any AEs in the subject's source documents and on the AE section of the CRF.
- Issue an e-diary and provide instructions on its use for 7 days (Day 1 through Day 7, where Day 1 is the day of vaccination).
- Issue a measuring device and a digital thermometer and provide instructions on their use for 7 days (Day 1 through Day 7, where Day 1 is the day of vaccination).

- Ask the parent(s)/legal guardian(s)/caregiver(s) to contact the site staff or investigator immediately if the subject experiences redness or swelling at the injection site measuring greater than 7 cm (>14 measuring device units) from Day 1 to Day 7 after vaccination to determine if an unscheduled reactogenicity visit is required.
- Ask the parent(s)/legal guardian(s)/caregiver(s) to contact the investigator immediately if any significant illness or hospitalization occurs during the study period.

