8.1.4. Time Period for Collecting AE/SAE Information

The time period for actively eliciting and collecting AEs and SAEs (“active collection period”) for each subject begins from the time the subject/parent(s)/legal guardian(s) provides informed consent, which is obtained before the subject’s participation in the study (ie, before undergoing any study-related procedure and/or receiving investigational product), through and including Visit 2.

For subjects who are screen failures, the active collection period ends when screen failure status is determined.

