3. ENDPOINTS AND BASELINE VARIABLES: DEFINITIONS AND CONVENTIONS

3.1. Primary Endpoints

- Local reactions within 7 days after vaccination.
- Systemic events within 7 days after vaccination.
- Adverse events (AEs) within 1 month after vaccination.

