6.3.1. Adverse Events

It should be recognized that most studies are not designed to reliably demonstrate a causal relationship between the use of a pharmaceutical product and an AE or a group of AEs. Except for select events in unique situations, studies do not employ formal adjudication procedures for the purpose of event classification. As such, safety analysis is generally considered as an exploratory analysis and its purpose is to generate hypotheses for further investigation.

Descriptive summaries and listing of AEs will be provided. The descriptive statistics for AEs will be summarized as the number and percentage of subjects reporting at least 1 event of each preferred term with associated Clopper-Pearson 95% CIs ([Section 5.2.1](#)), arranged by system organ class, and will also be summarized as the number of occurrences of the events.

For the safety results in children 6 to 17 years of age in India, the exact 2-sided 95% CIs will be provided for AEs within 1 month after vaccination.

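### SAP 6.1.1.1 starts the primary adverse-event window at consent, while the endpoint it analyses starts at vaccination

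*SAP*

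**What the plan says.** Protocol section 2 gives the primary AE endpoint as "AEs within 1 month after vaccination". SAP 3.1 repeats it: "Adverse events (AEs) within 1 month after vaccination". SAP 6.3.1 keeps to that window when it commits to intervals: "the exact 2-sided 95% CIs will be provided for AEs within 1 month after vaccination".

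SAP 6.1.1.1 names the SAP 3.1 endpoints as the ones it analyses. Under its analysis time points for AEs and SAEs, however, it gives a different start: "from the signing of the informed consent document (ICD) to 1 month after vaccination".

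Elsewhere a consent start appears only as a rule for collecting data. Protocol 8.1.4 says the active collection period "begins from the time the subject/parent(s)/legal guardian(s) provides informed consent" and runs through Visit 2. Among the Visit 1 procedures, ahead of vaccine administration, protocol 6.1 has the site "Collect and record any AEs and serious adverse events (SAEs) that occurred since the signing of the ICD".

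The analysis population is defined in SAP 4.2: "The safety population will include all subjects who receive 1 dose of an investigational product".

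**The concern.** The SAP gives two start points for one primary endpoint. A programmer following 6.1.1.1 would include AEs with onset between consent and the dose; one following 3.1 and 6.3.1 would leave them out. The two tables could differ while both comply with the SAP.

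The study is single-arm and descriptive, so the AE proportion and its exact interval are the result. The only objective is to describe the safety profile of the vaccine, and an event that began before the injection says nothing about that. The consent-start window can only leave the proportion unchanged or raise it. A single extra subject shows most when AEs are few, and protocol 1.2 reports that no AEs were reported by caregivers at the 1-month visit in the earlier Indian study of 200 subjects of this age.

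**Working it through.** **Step 1. Set the passages side by side.**

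| Place | Role of the text | Start of AE window |
|---|---|---|
| Protocol 2 | Endpoint definition | Vaccination |
| SAP 3.1 | Endpoint definition | Vaccination |
| SAP 6.3.1 | Exact CIs for AEs | Vaccination |
| SAP 6.1.1.1 | Analysis time point for the SAP 3.1 endpoints | Consent |
| Protocol 8.1.4, 6.1 | Data collection | Consent |

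Protocol 9.2 gives no AE window. SAP 6.1.1.1 is the only analysis text with a consent start.

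**Step 2. Could pre-dose events reach the table?** They are collected (protocol 6.1). The safety population leaves out subjects who were never vaccinated, so AEs in screen failures do not enter, but it keeps every recorded event of a vaccinated subject. Neither document defines treatment-emergent AEs or separates pre-dose onsets. SAP 6.3 refers to sponsor reporting standards, which are not shown.

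**Step 3. Was a wider window intended?** SAP section 2 requires a major change to the primary endpoint or its analysis to appear in a protocol amendment as well. The SAP is version 1 and lists no changes. Nothing shows an intended change.

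**Step 4. The plan's own figure.** Protocol 9.1 gives the probability of seeing at least 1 AE at a true rate of 1.0% with N = 100: 1 − (1 − 0.01)^100 = 63.4%, as printed. The other numeric cells of Table 4 also reproduce. This figure does not depend on the window.

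**Step 5. Effect of one misplaced subject.** With N = 100 (protocol 3.3), one subject counted only for a pre-dose AE moves the proportion by 1/100 = 1 percentage point. The AE counts below are illustrative. Intervals are Clopper-Pearson (SAP 5.2.1), with lower limit the 2.5% quantile of Beta(r, n − r + 1) and upper limit the 97.5% quantile of Beta(r + 1, n − r), which is equivalent to the F form in the SAP.

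| Post-vaccination only | Exact 95% CI | With one pre-dose subject added | Exact 95% CI |
|---|---|---|---|
| 0/100 | 0 to 3.62% | 1/100 | 0.03 to 5.45% |
| 5/100 | 1.64 to 11.28% | 6/100 | 2.23 to 12.60% |
| 10/100 | 4.90 to 17.62% | 11/100 | 5.62 to 18.83% |

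**Step 6. How often would it happen?** The documents give neither the consent-to-dose gap nor an AE rate for this period, so both are assumed. Let p be the 28-day AE risk and g the gap in days, with a constant hazard h = −ln(1 − p)/28. The pre-dose risk per subject is q = 1 − exp(−h·g), and the chance of at least one such subject in 100 is 1 − (1 − q)^100.

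Example: p = 20% and g = 6/24 = 0.25 day give h = 0.00797 per day, q = 0.199% and a chance of 18.1%.

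| Gap | p = 2% | p = 5% | p = 10% | p = 20% |
|---|---|---|---|---|
| 1 h | 0.30% | 0.76% | 1.56% | 3.27% |
| 3 h | 0.90% | 2.26% | 4.59% | 9.48% |
| 6 h | 1.79% | 4.48% | 8.98% | 18.06% |

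The expected number of affected subjects, 100·q, runs from 0.003 to 0.20.

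**The case against.** The strongest reply is that this is a template slip already covered elsewhere. SAP 6.1.1.1 imports the SAP 3.1 endpoints rather than redefining them, its consent start matches the protocol's collection period, and SAP 6.3.1 plans the post-vaccination intervals. The post-vaccination result is indeed planned, and that limits the harm. It does not settle the matter: 6.1.1.1 labels its window as an analysis time point for the primary endpoint, so 6.3.1 is the other side of the conflict.

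A second reply is that the sponsor's reporting standards may filter out pre-dose onsets. They may; the documents do not show it. If they do, the output would depart from the literal text of 6.1.1.1, which would still need correcting.

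A third is that the upper end of the probability range is too high. If the earlier Indian study is taken as 0 of 200 with an AE, the exact 95% upper limit is 1.83%, and the formula in step 6 then gives about 0.27%, 0.82% and 1.6% for gaps of 1, 3 and 6 hours. This is fair, although AEs may have been elicited differently there. In the other direction, protocol 4.3 lets vaccination be delayed for a temporary illness, which could make some gaps longer than 6 hours. The 0.3 to 18% range is therefore an illustration and not a bound.

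Finally, counting extra events errs on the cautious side for safety. That is true of the direction, but a descriptive estimate should still measure its stated endpoint.

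**Conclusion.** The concern holds as a minor inconsistency. SAP 6.1.1.1 is wrong as written for the endpoint it cites, and followed literally it counts pre-dose AEs of vaccinated subjects in the primary proportion.

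The numerical effect is likely to be nil or one subject: consent and dosing are normally both Visit 1 procedures, and under the assumptions above most studies of this size would have no affected subject. The size of 1 percentage point per affected subject needs no assumption beyond N = 100. The frequency rests wholly on the assumed gap, AE risk and constant hazard. SAP 5.1 has no hypothesis test or decision rule, so none is affected, and the sample-size table is unchanged.

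Confidence is high that the texts conflict. Whether pre-dose events would actually be counted depends on reporting standards that are not shown.

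**What to change.** In SAP 6.1.1.1, start the window for the primary AE proportion and its exact CI at vaccination, so that only AEs with onset after the dose count. List AEs from consent to vaccination separately.

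State how Day 1 events are placed. Protocol section 6 says "the day of vaccination should be considered Day 1", so an onset date alone cannot split that day. The pre-dose AE collection at Visit 1 or an onset time can do so. SAP 6.3.4 already needs AEs located within the 20 minutes after the dose, so the CRF may hold this information; that should be confirmed.

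The cost is one SAP line and one listing, with no change to the protocol endpoint and no added visit. If the CRF cannot tell a pre-dose from a post-dose event on Day 1, it needs one indicator or an onset time.

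Optionally, the same edit could say whether 1 month means through Visit 2 or a given day number. The correction does not depend on this.

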6.2. Baseline and Other Summaries and Analyses

6.2.1. Demographic, Medical History, and Baseline Summaries

Descriptive summary reports for demographic characteristics will be provided for the FAS and safety analysis populations. Descriptive summary reports for medical history will be provided for the safety population only.

6.2.2. Study Conduct and Subject Disposition

The number and percentage of subjects who are vaccinated will be included in the subject disposition summary: subjects who withdraw during the vaccination phase, complete the vaccination phase, complete the study, and withdraw during the follow-up phase will be summarized. The reasons for withdrawal will also be tabulated. The reasons for withdrawal will be those specified in the database; no rewording/recoding will be done.

The number and percentage of subjects vaccinated will be tabulated.

A listing of noncompliant vaccine administration will be provided. The protocol deviations will also be listed. A listing of subjects who withdrew because of AEs will be provided.

All assigned subjects will be used to generate these tables. Subjects who sign the ICD but are screen failures will be also summarized.

